Most research demonstrating the general anti-inflammatory effects of LDN have been completed in animal models, but there are some pilot studies demonstrating this effect in humans as well. Multiple pilot studies have demonstrated decreased levels of inflammatory markers in women with fibromyalgia following administration of LDN.^{5,7,18} Fibromyalgia (similar to endometriosis) is considered an inflammatory disorder. One study demonstrated that women with fibromyalgia and an elevated erythrocyte sedimentation rate (ESR), which is a serum marker for inflammation, had improved response rates to LDN as compared to women with fibromyalgia and a normal ESR.⁷ A separate 10-week crossover trial using LDN in women with fibromyalgia demonstrated significantly decreased plasma concentrations of multiple key pro-inflammatory cytokines as well as a 15% reported decrease in fibromyalgia associated pain.¹⁸

In summary, endometriosis is a devastating disease that impacts nearly 1:10 women in the reproductive years or their life. The pathophysiology of endometriosis is not completely understood, however, there is strong evidence that inflammation plays a major role in the symptoms associate with endometriosis. Current strategies for the management of endometriosis-associated pain often leave women seeking additional relief in the form of opioid-based treatments. In light of the current opioid epidemic it is important that we continue seek non-opioid based therapies that can provide symptomatic relief while we continue to try and better understand this debilitating disease. LDN has gained some popularity as an off-label treatment for inflammatory conditions such as multiple sclerosis, Crohn's disease and fibromyalgia, but the literature has nothing to offer in the way of significant randomized controlled trials to adequately test the mounting evidence that LDN is beneficial in chronic inflammatory conditions to include endometriosis.

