3.0 Inclusion and Exclusion Criteria

3.1 Inclusion Criteria

Inclusion

- Premenopausal female ages 18 to 45 years old on the day of signing informed consent.
- Must agree to use only study-specific analgesic medications during the study and is not known to be intolerant to them.
- Diagnosed with endometriosis and has had, within the last 10 years prior to signing the informed consent, surgical diagnosis with direct visualization and/or histopathologic confirmation of endometriosis.
- Is not expected to undergo gynecological surgery or other surgical procedures for treatment of endometriosis during the study period.
- Agrees to use contraception if not surgically sterile during the entire study.
- Patients using oral contraceptives, LARCs and/or GnRH agonists/antagonists for contraception and/or management of endometriosis, with a stable regimen, will be able to continue in the study, however, women using oral contraceptives and GnRH agonist/antagonists will be switched to Norethindrone acetate during the 1-2 week run-in period as prescribed by principle investigator.

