3.2 Exclusion Criteria

Exclusion

- Women that are pregnant, breastfeeding or trying to conceive.
- Patients with chronic daily opioid use and any chronic pain or frequently reoccurring pain condition, other than endometriosis, that is treated with opioids or requires analgesics for more than 7 days per month.
- Patients with abnormal liver function tests (greater than 3x normal limit) in the past year or history of liver disease. Routine screening of liver function is not required.
- Non-English speaking or inability to read and understand English secondary, in part, to the need to read and report daily results in English.
- Undiagnosed vaginal bleeding
- Patients with history of opioid, illicit drug or alcohol abuse
- Patients currently taking thioridazine
- Patients with a history of suicidality
- Patients with current or history of unstable depression or other psychiatric disorder who, by PI judgement, are unstable or not well controlled
- Known, suspected or history of cancer of the breast
- Active deep vein thrombosis, pulmonary embolism or history of these conditions
- Active or recent arterial thromboembolic disease (e.g., stroke, myocardial infarction)

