4.4 Eligibility/screening of subjects

When the study team receives information about a potential subject, follow-up is made to verify eligibility. If excluded, no further questions are asked and they are thanked for their time. If eligible the subject is scheduled for a visit.

Follow-up includes a phone screen of the potential subject by asking questions such as, ensuring the subject is premenopausal and in between the ages of 18 and 45 years old, agree to only use study-specific analgesic medications during the study and if intolerance to oxycodone and ibuprofen are known, agrees to use Norethindrone acetate and either their LARC or other barrier contraception while in the study, if the subject plans on becoming pregnant or trying to conceive at any point during the study, if the subject has any chronic daily narcotic use and any chronic pain other than endometriosis, and verify the subject is able to speak and read English to answer the surveys. We will also confirm that the subject is willing and able to be reliably contacted by email for study specific purposes.

If the participant passes the phone screen, the participant will be scheduled for a screening visit. After consent and receiving Norethindrone acetate, an email will be sent for the subject to complete the daily surveys for next 6-7 days. Upon completion of the surveys, the participant will pass or fail the screening process.

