7.4.6.5 Prior and Concomitant Therapy

All concomitant medications will be documented. There are no prohibited medications or therapies throughout the study.

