11.0 Risks

Risks of Norethindrone: Serious adverse reactions with the use of norethindrone are serious cardiovascular events and stroke, vascular events, and liver disease. Adverse reactions commonly reported by norethindrone users are: Irregular uterine bleeding, nausea, breast tenderness, and headache

Risks of Low Dose naltrexone: Adverse reactions to low dose naltrexone can include hepatotoxicity, depression and suicidality, allergic reactions, eosinophilic pneumonia, muscle cramps, dizziness or syncope, somnolence or sedation, decreased appetite, and insomnia. Everyone taking part in the study will be watched carefully for side effects; however, doctors do not know all the discomforts and risks that may happen. With all drugs there is the possibility of complications and side effects that are not known at this time. These may be mild or serious, and in some cases may be very serious, long-lasting, or may never go away. There is also a risk of death.

If you experience any side effect (or other health issues) during this study, let your study doctor know immediately. If you are not honest about your side effects, you may harm yourself by staying in this study. If you do not understand what any of these side effects mean, please ask the study doctor or study staff to explain the words to you.

Common side effects of naltrexone at higher doses include:

- Nausea, vomiting, diarrhea or constipation
- Stomach pain or cramping
- Loss of appetite
- Headache
- Dizziness
- Nervousness, irritability, or anxiety
- Tearfulness
- Increased or decreased energy

This study plans on using low dose naltrexone at a much lower dose than typically available. Multiple studies have used similar doses of naltrexone (3 - 4.5 mg) in both adult and children with no significant adverse reactions. There is no evidence reported of interactions of low dose naltrexone with other medications. The most commonly reported side effects in studies using low dose naltrexone include:

- Difficulty falling and/or staying asleep (insomnia)
- Vivid dreams
- Headaches.

Though it is an uncommon event, there is a risk of unexpected allergic reaction to the study drug which may include hives, rash, swelling or difficulty breathing. If one of the mentioned symptoms appears, stop taking your study drug(s) and seek immediate medical help.

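### No eligibility criterion or phone-screen question names naltrexone use, or intolerance to either trial drug, so some women taking their own LDN could be randomised

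*Combined protocol and SAP*

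**What the plan says.** All references are to the combined protocol and SAP.

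- **Section 3.2** names one individual drug as an exclusion: "Patients currently taking thioridazine". It also excludes "Patients with history of opioid, illicit drug or alcohol abuse". A further bullet concerns chronic daily opioid use and chronic or recurrent pain, other than endometriosis, that is treated with opioids or needs analgesics on more than 7 days a month.
- **Section 3.1** has one rule on medicines and intolerance, and it is confined to analgesics: "Must agree to use only study-specific analgesic medications during the study and is not known to be intolerant to them".
- **Sections 4.4 and 5.1.2** describe the phone screen. The only intolerance question is "if intolerance to oxycodone and ibuprofen are known".
- **Section 7.4.6.5** says that concomitant medicines will be documented, and then: "There are no prohibited medications or therapies throughout the study".
- **Section 2.1** acknowledges use outside trials: "LDN has gained some popularity as an off-label treatment for inflammatory conditions". It names multiple sclerosis, Crohn's disease and fibromyalgia, and section 12.2 repeats the point.
- **Section 11.0** states that "there is a risk of unexpected allergic reaction to the study drug".

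**The concern.** Aim 1 in section 1.1 compares hormonal suppression plus LDN with hormonal suppression alone. A placebo participant who takes LDN from her own supply is not receiving the control condition, and an active-arm participant who does so is receiving the drug from two sources. In neither case does randomisation create the intended difference in exposure.

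If she stops at entry, the problem is different. Her pre-intervention week may be recorded on the drug or just after it, which bears on the pre/post secondary analysis in section 8.3. In the placebo arm, carry-over or withdrawal may also enter the 12-week primary outcome.

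The analysis would not correct for this. Non-study LDN would be recorded as a concomitant medicine, but the daily report is described in terms of NSAIDs and opioids (sections 1.3 and 7.1), and the primary model adjusts only for opioid intake.

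The intolerance gap is separate and does not depend on how common LDN use is. A woman with a known reaction to naltrexone, or to the norethindrone acetate that both arms receive, meets every written criterion. If she reacts and is removed, section 3.3.2 says that no further data are collected on her, so an avoidable event also costs outcome data.

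**Working it through.** **Which rule would stop which woman**

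1. *Naltrexone for opioid or alcohol dependence.* Mostly excluded through the abuse-history criterion.
2. *Off-label LDN for pain.* The rule in 3.1 limits her to study analgesics, which section 7.2.2 gives as ibuprofen, acetaminophen and, on request, oxycodone. Read broadly, it bars her own LDN. It does not name LDN, and 7.4.6.5 says that nothing is prohibited. The outcome depends on how the site reads the two sections together.
3. *Off-label LDN for fibromyalgia or another pain condition.* The other-chronic-pain exclusion may apply. Its wording joins opioid use and other pain with an ambiguous conjunction, and whether LDN counts as an analgesic is not stated.
4. *Off-label LDN for a non-pain indication, such as Crohn's disease or multiple sclerosis.* No criterion applies.
5. *Recent user who has stopped.* No criterion applies. The 1-2 week run-in changes hormonal treatment and tests diary compliance; it is not described as a naltrexone washout.
6. *Known intolerance to naltrexone or norethindrone acetate.* No criterion applies.

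**The plan's own sample size (section 8.2)**

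Inputs: difference 10 mm, SD 20 mm, two-sided alpha 0.05, power 80%, withdrawal 20%, 80 randomised per arm.

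- Standardised effect: 10 / 20 = 0.5.
- The two-sample t-test needs 63.8, so 64 per arm.
- Allowing for withdrawal: 64 / (1 - 0.20) = 80 per arm, 160 in total. The stated figure reproduces.
- Power at 64 per arm: 80.1%.

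**Effect of women with no contrast**

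The share c of such women is not in the documents and is assumed here. Suppose the same share c in each arm has zero contrast: full LDN effect in the placebo arm, and nothing further gained in the active arm. The expected difference is then

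(1 - c) × 10 + c × 0 = 10 × (1 - c) mm.

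With SD 20 mm and n = 64 per arm, the noncentrality is [10(1 - c) / 20] × √(64/2):

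| c | Women among 160 | Difference (mm) | Noncentrality | Power |
|---|---|---|---|---|
| 0 | 0 | 10.0 | 2.828 | 80.1% |
| 1% | 1.6 | 9.9 | 2.800 | 79.3% |
| 2% | 3.2 | 9.8 | 2.772 | 78.5% |
| 5% | 8 | 9.5 | 2.687 | 76.0% |
| 10% | 16 | 9.0 | 2.546 | 71.4% |

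The last two rows show only how the result scales; nothing in the documents supports shares that high. At c = 2%, restoring 80% would take 67 completers per arm: 67 / 0.8 = 83.75, so 84 per arm and 168 randomised.

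**The case against.** The strongest reply is that existing rules already cover much of the group. The opening half of the analgesic criterion in 3.1 can fairly be read to bar LDN taken for pain, since section 2.3 presents LDN as a source of analgesic relief and the phone screen asks for the same agreement. The abuse-history and other-chronic-pain exclusions remove others. A reader might therefore infer too much from the silence of 3.2, namely that nothing at all excludes naltrexone users. The documents do not support that. What remains is chiefly LDN for non-pain conditions, recent users, and pain users at a site that follows 7.4.6.5.

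A reader might also infer that the comparison is lost for every such woman. It is lost only if she continues her own LDN. If she stops, it is blurred to an extent, and in a direction, that the documents do not settle.

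On size, section 2.1 speaks of limited popularity in other diseases, not in endometriosis. The calculation above is a worst case within each share c. Section 8.2 also keeps partial data from women who withdraw, so the effective number lies between 64 and 80 per arm. This stands, and it means that no material loss of power can be claimed.

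On intolerance, a medical history is taken at screening, the first study dose is taken with staff present, and norethindrone acetate is started before randomisation where needed, so some problems would surface early. These steps reduce the risk. They do not tell the site that a known reaction is a reason not to enrol.

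**Conclusion.** The gap is real but narrow. No criterion or screening question names naltrexone use, or intolerance to either trial drug, and 3.1 and 7.4.6.5 pull in different directions on whether a participant may take her own LDN. As written, the plan lets some women enter the placebo arm while taking the drug under test.

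The likely cost in power is about one to two percentage points (79.3% to 78.5%, against 80.1%, at 64 per arm). This assumes a 1% to 2% share, full loss of contrast in those women, and an unchanged SD of 20 mm. The share is an assumption and is probably low. It would be wrong to infer that the trial is materially underpowered for this reason.

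The case for a change rests on a control arm that is what Aim 1 says it is, and on avoiding a foreseeable safety risk. It is a cheap improvement.

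**What to change.** 1. In 3.2, add an exclusion for current or recent naltrexone use, with the interval set by the investigators.
2. In 3.2, add an exclusion for known hypersensitivity or intolerance to naltrexone or norethindrone acetate.
3. Add both items to the phone screen in 4.4, and to its description in 5.1.2.
4. Reconcile 3.1 with 7.4.6.5, so that the handling of non-study naltrexone during the trial is stated once and consistently. What that rule should be is for the investigators.

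The cost is two exclusion lines, two screening questions and one reconciled paragraph. The sample size does not change. The downside is the loss of a few otherwise eligible women.

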3.3 Early Withdrawal of Subjects

3.3.1 Criteria for removal from study

Subjects will be removed from the study for safety reasons. Subjects will be evaluated for potential negative reactions to study medications at each visit. Additionally, subjects will be advised to contact the study team with any new negative symptoms to arrange evaluation.

Additionally, unintended pregnancy during the study period will meet criteria for withdrawal from the study.

Withdraw of consent at any time during the study period will also constitute the withdrawal of study subjects.

3.3.2 Follow-up for withdrawn subjects

The statistical methods allow for withdraw/screen fails. Subjects will be asked to return the study drug to the site if withdrawn or removed from the study. No other safety follow-up planned.

If the subject is removed from the study for any of the above reasons, she will receive the appropriate treatment based on the decisions of her providing physician team. No further data will be collected on these patients.

4.0 Recruitment Methods

4.1 Identification of subjects

Potential subjects will be identified within our Minimally Invasive Gynecological (MIGS) Division Outpatient clinic location and others identified as having endometriosis within PennState Women's Health department. We have created an endometriosis database, which we use to screen potential subjects that may qualify for this study. We will also utilize an approved flyer, patient recruitment letter, StudyFinder and EIM report request to identify potentially eligible subjects. In addition, we have developed a MIGS Research Patient Form to give clinic patients at their intake to gauge potential interest in any current studies within the Minimally Invasive Gynecologic Surgery Division.

4.2 Recruitment process

Subjects will be recruited from various MIGS and Women's Health clinic locations within Penn State Health. Participation will be purely voluntary. Subjects will be compensated for their time and effort. Written informed consent will be obtained prior to the study. We will use a study coordinator to assist us with contacting patients for their follow up visits and completing their surveys.

We do not anticipate having any difficulty recruiting these women into the study given our extensive experience with this to date. We are currently one of the highest volume Minimally Invasive GYN Surgery groups in the region. In 2016 we had 2700 patient encounters for endometriosis/female pelvic pain. Additionally, 80% of these encounters involved patients located within 10 counties that included Dauphin County and those counties adjacent to Dauphin County within the Penn State Health region. The close proximity of the patients will help increase the likelihood of patient participation. In the past 12 months has seen 275 new patient consults, with nearly 900 total clinic visits and over 950 surgical procedures performed specifically for endometriosis or pelvic pain.

We will meet on a regular basis to discuss how well we are doing with recruitment and retention. We have designed an easy to follow study, thus we do not anticipate difficulty with retaining these subjects. Based on our previous clinical trials involving women with endometriosis, we assume an 80% retention rate and we will recruit an average of 64 subjects per year.

4.3 Recruitment materials

The PI will monitor recruitment and retention rates for the study monthly to ensure that the goals are being met. In addition, we will collaborate with the Penn State Clinical Trials Office and Office of Marketing and Communications to promote the study and increase recruitment efforts. IRB approved flyers will be hung in our Minimally Invasive GYN Surgery and around campus at approved locations. The MIGS Research Patient Form will be given to patients at their clinic visits, collected by clinic staff, and then forwarded to study coordinators to contact patients with applicable study information. Patient recruitment letters will be sent to previous study participants with endometriosis who wished to be contacted for future research opportunities to start. The letter will also be used to provide study information to all identified endometriosis patients within PennState Women's Health (via EIM request).

We will also utilize StudyFinder, which is an online database that connects interested volunteers with a variety of studies, which University researchers are conducting. Visitors can browse by topic or search for a keyword to discover available studies at Penn State Hershey Medical Center. StudyFinder is also promoted to the community through Web advertising, Google search and billboards. We will also register this study at ClinicalTrials.gov. If recruitment and retention are inadequate, we will begin to advertise in the broader central Pennsylvania area and with offices known to refer endometriosis patients to our practice.

4.4 Eligibility/screening of subjects

When the study team receives information about a potential subject, follow-up is made to verify eligibility. If excluded, no further questions are asked and they are thanked for their time. If eligible the subject is scheduled for a visit.

Follow-up includes a phone screen of the potential subject by asking questions such as, ensuring the subject is premenopausal and in between the ages of 18 and 45 years old, agree to only use study-specific analgesic medications during the study and if intolerance to oxycodone and ibuprofen are known, agrees to use Norethindrone acetate and either their LARC or other barrier contraception while in the study, if the subject plans on becoming pregnant or trying to conceive at any point during the study, if the subject has any chronic daily narcotic use and any chronic pain other than endometriosis, and verify the subject is able to speak and read English to answer the surveys. We will also confirm that the subject is willing and able to be reliably contacted by email for study specific purposes.

If the participant passes the phone screen, the participant will be scheduled for a screening visit. After consent and receiving Norethindrone acetate, an email will be sent for the subject to complete the daily surveys for next 6-7 days. Upon completion of the surveys, the participant will pass or fail the screening process.

5.0 Consent Process and Documentation

5.1 Consent Process

5.1.1 Obtaining Informed Consent

5.1.1.1 Timing and Location of Consent

In accordance to HRP-090 SOP for the Informed Consent Process, the potential subject will be given a copy of the most current approved consent document for review in advance. The consent process will take place in a private room setting in the clinic or the Clinical Research Center (CRC). The consent document will be

provided for review and discussion will take place. Consent will be obtained prior to any study procedures being done.

5.1.1.2 Coercion or Undue Influence during Consent

The subject will be informed that their participation in the study is voluntary. The subject will receive a copy of the consent form to read at home prior to making a screening appointment. At the time of consent, all sections of the informed consent will be thoroughly reviewed with the subject and all of the subject's questions will be answered prior to signing. Once all questions have been answered and the subject verbalizes understanding of the study and its requirements and agrees to participate, the subject and coordinator sign the consent form. A copy of the signed consent form is provided to the subject.

